2.0 TRIAL DESIGN

2.1 Trial Design

This is a single arm phase II pilot study evaluating the efficacy of single-agent pembrolizumab for untreated, indolent B-cell non-Hodgkin lymphoproliferative diseases (iBCL) including follicular lymphoma (FL) and marginal zone lymphoma (MZL). In the window phase, treatment will be administered for up to six 3-week cycles and a response assessment performed at the conclusion. Patients that tolerate the drug and meet criteria for an objective response after 6 cycles may continue to receive pembrolizumab for up to an additional 12 cycles in the continuation phase. Patients who show progressive disease or stable disease after 6 cycles may be restaged after 3 additional cycles to assess for pseudoprogression/delayed response. Patients who show disease progression after 3 additional cycles will be removed from treatment. Patients who do not show evidence of disease progression may continue to receive pembrolizumab for up to a total of 18 cycles. A futility analysis will be performed after the first 5 subjects in each of two histologic subgroups (follicular lymphoma, marginal zone lymphoma) are treated. We anticipate that subjects will be enrolled over approximately 18 months and will be followed for outcomes for up to 5 years using standard-of-care assessments.

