8.2 Statistical Analysis Plan

We shall use the backbone of a Simon two-stage minimax design for this trial with an additional look to potentially stop for futility based on outcomes observed in two specific histology subgroups (follicular lymphoma, marginal-zone lymphoma). With 33 patients, a Simon two-stage minimax design yields 90% to observe an ORR that is statistically significantly higher (at the one-sided significance level of .05) than the fixed ORR rate of 25% if the assumed-true ORR with the regimen currently proposed is 50%. In the first stage, if we observe 4 or fewer responses among 16 patients (25% or less), consideration will be given to terminating the study due to lack of sufficient efficacy. On the other hand, if 5 or more responses are seen among the first 16 patients (and observed ORR of at least 31%), an additional 17 patients will be enrolled. At this point, if 13 or more responses are seen among the 33 patients (an observed rate of at least 39%), the study will conclude that the proposed treatment is potentially efficacious and worthy of further study.

The modification to the above Simon two-stage design will include an interim look within the first stage, with this interim look consisting of subtype-specific analyses. If there are 0 responses among the first 6 patients with follicular lymphoma, accrual of such patients will be stopped. The same rule will be applied to patients with marginal-zone lymphoma. If the true probability of response is 50%, the probability of seeing 0 responses among 6 patients is .016. This additional look has a small impact on the power of the Simon design (since, under the alternative hypothesis, we may incorrectly stop at least one group for futility, hence decreasing the power (i.e., increasing the Type II error or false negative rate). In particular, if one assumes a 50% ORR (consistent with the alternative hypothesis in the Simon design) in both subtypes with an equal probability of enrollment to each subtype, the addition of the subtype-specific rules from above decreases the power from 90% to approximately 87% (estimated from 5,000 simulations). Note that if in each subtype there are 0 responses in the first 6 patients, for a total of 0/12, these results would lead to stopping the trial per the Simon two-stage rules as it would not be possible to achieve at least 5 responses in the first 16 patients.

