If the study is stopped due to lack of efficacy in a histologic subgroup, the study may only be reopened to accrual for patients with that histology with modifications (e.g. addition of a

second agent, change in dosing, etc) that have been reviewed and approved where appropriate by the sponsor, scientific review, and relevant regulatory bodies.

Suspension rules for toxicity:

Prior studies treating patients that have not received prior chemotherapy suggest that the rates of grade ≥ 3 immune-related AEs occur in approximately 10% of patients (Reck et al, NEJM 2016). Infusion reactions of \geq grade 3 are less common and less consistently reported in publications. For this reason, we will initiate a suspension rule for infusion- or immune-related AEs of \geq grade 3 of up to 12%. This will be deemed to occur if the lower level of a one-sided 80% confidence interval for immune-related or infusional AEs of \geq grade 3 exceeds 12%.

Operationally, the study will be suspended and referred to the DSMC for consideration of results and appropriate modification or termination of the study if

- 3 out of the first 11 or fewer, 5 out of the first 22 or fewer, 6 out of the first 33 or fewer have \geq grade 3 immune related or infusional AEs

If the true probability of \geq grade 3 AEs is 5%, the probability of suspending the trial due to excess AEs after 11, 22, and 33 patients is approximately <0.02, 0.02, and 0.02, respectively. If the true probability of \geq grade 3 AEs is 30%, the probability of suspension due to excess AE is approximately 0.80, 0.94, and 0.99, respectively. (Probabilities of suspension estimated from 5,000 simulations).

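### Section 2.1 puts the histology futility look after 5 patients and Section 8.2 after 6; the 6-patient rule has power of about 89–90%, not the stated 87% or so.

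*Combined protocol and SAP*

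**What the plan says.** Section 2.1 (Trial Design): "A futility analysis will be performed after the first 5 subjects in each of two histologic subgroups". It gives no response threshold.

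Section 8.2 builds on a Simon two-stage minimax design: stop at 4 or fewer responses in 16 patients, otherwise enrol 17 more and call the treatment promising at 13 or more responses in 33. It opens "With 33 patients, a Simon two-stage minimax design yields 90% to observe an ORR" above 25% when the true rate is 50%. The added modification "will include an interim look within the first stage": "If there are 0 responses among the first 6 patients with follicular lymphoma, accrual of such patients will be stopped", and "The same rule will be applied to patients with marginal-zone lymphoma". The section gives .016 as the chance of no response in six at a 50% rate. It also considers the case "if in each subtype there are 0 responses in the first 6 patients, for a total of 0/12".

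On cost, Section 8.2 says that, with 50% response in both subtypes and equal enrolment, the added rule "decreases the power from 90% to approximately 87% (estimated from 5,000 simulations".

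On consequence, once a histology has been stopped, "the study may only be reopened to accrual for patients with that histology with modifications", and these must be reviewed and approved.

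**The concern.** Two things looked wrong.

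First, the look falls at the fifth patient in one section and at the sixth in the other. This is a decision rule that ends accrual to a histology, and reopening needs an approved modification. A reader of Section 2.1 and a reader of Section 8.2 would act at different points.

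Second, the stated loss of about 3 points of power looked too large for the 6-patient rule. Wrong closure of a subtype is rare at a 50% response rate, and a trial that starts with 0/6 in one subtype is already more likely than average to fail the Simon rules. The power actually lost should therefore be smaller than the chance of a wrong closure.

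Section 8.2 also does not say whether a closed subtype's places pass to the other subtype, or how the 13-of-33 criterion applies if they do not. The power of the design depends on the answer.

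**Working it through.** **Inputs, all from Section 8.2.** Null response rate 25%, alternative 50%; continue at ≥5/16; success at ≥13/33; each patient equally likely to be either subtype; subtype closed at 0/6. The 5-patient look comes from Section 2.1. Applying the zero-response threshold at 5 is an assumption, because Section 2.1 states none.

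**Step 1: the base design reproduces.** The probability of success is the sum over x = 5 to 16 of P(Bin(16, p) = x) × P(Bin(17, p) ≥ 13 − x).
- p = 0.25: 0.0449, within the stated .05.
- p = 0.50: 0.9017, the stated 90%.

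**Step 2: which look size the Section 8.2 figures fit.**
- 0.5⁶ = 0.0156, the stated .016. For five patients, 0.5⁵ = 0.031.
- Two subtypes at 6 each make the 12 in 0/12; two at 5 would make 10.

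Both figures fit 6.

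**Step 3: closure probabilities.**

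| Look | One subtype closed, 50% ORR | At least one closed, 50% ORR | One subtype closed, 25% ORR |
|---|---|---|---|
| 0/6 | 0.5⁶ = 1.6% | 1 − (1 − 0.0156)² = 3.1% | 0.75⁶ = 17.8% |
| 0/5 (assumed threshold) | 0.5⁵ = 3.1% | 1 − (1 − 0.03125)² = 6.2% | 0.75⁵ = 23.7% |

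These take both subtypes as reaching the look.

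**Step 4: exact power with the added rule.** An exact recursion over 33 enrolment places tracks, for each subtype, the number enrolled, whether any response has occurred and whether the subtype is closed, together with total responses. Where places are lost, 13 responses are still required. The first figure in each cell limits the look to the first 16 patients; the second lets it fall at any time.

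| Handling of a closed subtype's places | 0/6 rule | 0/5 rule (assumed threshold) |
|---|---|---|
| Filled by the other subtype up to 33 | 0.9017 / 0.9017 | 0.9017 / 0.9017 |
| Lost | 0.8886 / 0.8872 | 0.8679 / 0.8668 |
| Any closure counted as failure | 0.8877 / 0.8858 | 0.8655 / 0.8640 |

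**Step 5: the floor.** No handling of closed places can lose more than every trial in which a closure occurs, so 0.8858 is the lowest power the 0/6 rule can have under the stated assumptions. The largest loss is 0.9017 − 0.8858 = 0.0159. That is about half of the 3.1% in Step 3, because only about half of the trials with a closure would otherwise have passed. The plan states a loss of about 3 points.

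**Step 6: could simulation error explain it?** The standard error with 5,000 runs is √(0.8858 × 0.1142 / 5000) = 0.0045. The chance of an estimate below 0.875, which would round to 87%, is 0.8% if true power is 0.8858 and 0.1% if it is 0.8886.

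**Step 7: candidate origins.** A 0/5 rule without filling gives 86.4–86.8%. Subtracting the 0/6 closure probability from the base power gives 0.9017 − 0.0310 = 0.871. Either would be reported as about 87%, and the documents do not let one choose between them.

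**Step 8: type I error.** At 25% response, the 0/6 rule has type I error between 0.0431 and 0.0449 across all the variants.

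**The case against.** The conflict between 5 and 6 has no answer in the documents. The power figure can be defended on several grounds.

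Section 8.2 says a wrong stop lowers power. If the other subtype filled every place at the same 50% rate, power would stay at 90.2%, so the text's own reasoning suggests its simulation did not fully fill. On that reading the gap is 1.6 to 1.9 points, against a figure given as approximate and taken from simulation. This is fair, and it makes the no-filling values the more natural comparison. It does not rescue 87%: the floor is 88.6% however closed places are treated, and simulation error would give a figure that low less than 1% of the time. The filling case also cannot be set aside, because Section 8.2 states the second stage and the final criterion in terms of 17 further patients and 33 in total.

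The 87% may simply belong to a 5-patient version of the rule, making this one discrepancy rather than two. That is possible but remains an inference. If it is so, not every figure in Section 8.2 points to 6, which is why the sponsor must confirm the look size.

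Finally, Section 8.2 already places the look within the first stage, so its timing is partly answered. What is unsaid is what happens when a subtype has fewer than 6 of the first 16 patients. With equal enrolment this has probability 2 × P(Bin(16, 0.5) ≤ 5) = 21%. It is a missing detail, and the conclusion does not depend on it.

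**Conclusion.** The concern holds. The look size is contradictory in current text, and the rule it governs closes accrual to a histology. The power stated for the 6-patient rule is too low: exact power is 88.6–88.9% without filling and 90.2% with filling, against approximately 87%, a gap of 1.6 to 3.2 points. This rests on Section 8.2's own assumptions of 50% response in both subtypes, equal enrolment and unchanged 5/16 and 13/33 boundaries. The comparison with a 5-patient rule further assumes that the zero-response threshold applies there.

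The error is conservative and does not threaten the design: type I error is 4.3–4.5% and the sample size stands. It should be corrected as a matter of consistency and of stated power.

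**What to change.** - Use one look size in Sections 2.1 and 8.2, and give the zero-response threshold in both. Six fits the .016 and 0/12 already in Section 8.2; the sponsor should confirm it.
- State in Section 8.2 whether a closed subtype's places are filled by the other subtype up to 33 and, if not, how the 13-of-33 criterion applies.
- Restate the power for the rule as then written. For 0/6 it is about 90% with filling and about 89% without. If 5 is chosen instead, the .016 and 0/12 must change as well.
- It would also help to say whether the look still applies when a subtype's sixth patient enrols after the sixteenth patient overall.

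If 6 is confirmed, the cost is one number in Section 2.1, two or three sentences in Section 8.2 and one short recalculation. The sample size does not change.

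### The toxicity suspension counts match the plan's 80% confidence criterion at 11, 22 and 33 patients but not at 12–19 or 23–26, so the definition and the operating rule need to be reconciled and the suspension probabilities recomputed.

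*Combined protocol and SAP*

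**What the plan says.** Section 8.2, under the suspension rules for toxicity, sets a limit of 12% for grade 3 or higher infusion-related or immune-related adverse events and defines when it counts as exceeded: "This will be deemed to occur if the lower level of a one-sided 80% confidence interval" for these events lies above 12%. The interval method is not named.

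The next sentence turns this into a rule: "Operationally, the study will be suspended and referred to the DSMC for consideration of results" if the number of patients with such events reaches "3 out of the first 11 or fewer, 5 out of the first 22 or fewer, 6 out of the first 33 or fewer". Read as written, the suspension count is 3 for up to 11 patients, 5 for 12 to 22 and 6 for 23 to 33. No step uses a count of 4.

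The section then gives the chance of suspension after 11, 22 and 33 patients, from 5,000 simulations. At a true rate of 5% it "is approximately <0.02, 0.02, and 0.02, respectively". At 30%, "the probability of suspension due to excess AE is approximately 0.80, 0.94, and 0.99, respectively".

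**The concern.** The definition and the counts stand side by side, and the second is presented as the working form of the first. The definition carries no schedule of looks, and the *or fewer* wording makes each count apply at every smaller number of patients in its step. A count that is the minimum at the end of a step is generally too high earlier in that step, because fewer patients need fewer events for the same lower limit. There may therefore be results that the plan's definition calls excessive and its operating rule lets pass.

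This is the trigger for suspension and referral to the DSMC. Apart from it, section 10.1 provides for DSMC review at least annually and as needed, while section 1.0 expects enrollment to take 18 months. A later trigger could mean more patients treated before the committee sees the result.

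**Working it through.** **Inputs (section 8.2).** One-sided 80% lower limit; threshold 12%; counts 3, 5 and 6 at up to 11, 22 and 33 patients; maximum 33 patients. Assumption: the exact (Clopper-Pearson) limit, since no method is named.

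**Formula.** For x patients with events among n, the limit L(x, n) is the 20th percentile of a Beta(x, n − x + 1) distribution. L exceeds 0.12 exactly when P(X ≥ x | n, 0.12) is below 0.20.

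**1. The plan's counts at the step ends.**

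| n | listed count: L | one fewer: L |
|---|---|---|
| 11 | 3: 14.3% | 2: 7.6% |
| 22 | 5: 14.4% | 4: 10.6% |
| 33 | 6: 12.04% | 5: 9.5% |

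The counts reproduce: each is the smallest that meets the criterion at its own n.

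**2. Smallest count meeting the criterion at every n.**

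| n | criterion needs | listed rule needs | limits |
|---|---|---|---|
| 1 | 1 | 3 | 1/1: 20.0% |
| 2–6 | 2 | 3 | 2/6: 14.0%; 2/7: 11.95% |
| 7–11 | 3 | 3 | agree |
| 12–13 | 3 | 5 | 3/12: 13.1%; 3/13: 12.04% |
| 14–19 | 4 | 5 | 4/14: 16.9%; 4/19: 12.3% |
| 20–22 | 5 | 5 | agree (4/20: 11.7%) |
| 23–26 | 5 | 6 | 5/23: 13.7%; 5/26: 12.1% |
| 27–33 | 6 | 6 | agree (5/27: 11.65%) |

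At n = 13 a count of 4 (limit 18.2%) also passes without suspension. All the listed discordant results after patient 11 can be reached without an earlier suspension. For example, 2 events in the first 11 and a third at patient 12 gives 3/12.

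**3. Interval method.** Other one-sided 80% intervals also leave a gap after patient 11: Wald at n = 12–20 and 23–27; Wilson, Jeffreys and Agresti-Coull at n = 12–22 and 23–29.

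**4. Size.** The event count was followed exactly patient by patient, with the boundary applied after each. The comparison follows the criterion but keeps the listed minimum of 3 events: 3 up to n = 13, 4 up to 19, 5 up to 26, 6 up to 33.

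| true rate | by patient | listed | criterion, floor 3 |
|---|---|---|---|
| 10% | 33 | 0.16 | 0.21 |
| 12% | 33 | 0.27 | 0.33 |
| 20% | 19 | 0.46 | 0.61 |
| 20% | 26 | 0.57 | 0.70 |
| 20% | 33 | 0.72 | 0.76 |
| 30% | 19 | 0.80 | 0.89 |
| 30% | 33 | 0.966 | 0.973 |

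The chance that the criterion is met at some n from 12 to 26 while the listed counts do not suspend is 0.15, 0.30 and 0.25 at true rates of 12%, 20% and 30%. The chance that this happens and the trial is never suspended is 0.06, 0.04 and 0.01.

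**5. The plan's suspension probabilities.** At 5% the listed rule gives 0.015, 0.017 and 0.020, which agrees with the text. At 30% it does not. At n = 11:

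1 − (0.7¹¹ + 11 × 0.3 × 0.7¹⁰ + 55 × 0.3² × 0.7⁹) = 1 − (0.0198 + 0.0932 + 0.1998) = 0.687.

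The three values are 0.687, 0.869 and 0.966, against the stated 0.80, 0.94 and 0.99. Simulation error cannot explain this: with 5,000 runs the standard error at 0.687 is √(0.687 × 0.313 / 5,000) = 0.007. A true rate of 35% gives 0.800, 0.944 and 0.992, which fits the stated values. The cumulative figures at 11, 22 and 33 are the same whether the counts are checked after every patient or only at those three points, because the count is constant within a step.

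**The case against.** The strongest reply is that the criterion was set for three looks. The counts are exact minima at 11, 22 and 33, and the probabilities are quoted at those same points. On that view *or fewer* only permits an earlier suspension once the count for the coming look has been reached, and there is no conflict. This is plausible and may be what was meant. But section 8.2 does not say it: the definition is unrestricted and the counts are introduced as its operational form. What stands is that naming the three looks would remove the inconsistency as well as changing the counts would.

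A reader might infer that the counts are wrong throughout patients 12 to 26. They are not: at 20–22 the count of 5 is what the exact criterion requires. A reader might also infer that the trial would run past its safety limit unchecked. The documents do not support that. A lower limit above 12% is a signal, not proof that the true rate is above 12%; most such trials are suspended later; and suspension means DSMC referral, not automatic termination. Other oversight also applies: ongoing review of adverse events (8.3.2.4), early termination for the incidence or severity of reactions (5.8), and committee review of adverse events and stopping rules (10.1). These reduce the consequence but do not replace a numerical trigger.

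It is also fair to say that a literal reading cuts both ways. Applied from the first patient with no floor, the criterion would suspend 29% of trials by patient 33 at a true rate of 10% and 9% at 5%, against 16% and 2% as listed. Any continuous version with a floor of 3 departs from the criterion at n = 1–6, and should say so.

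**Conclusion.** The inconsistency is real but limited. Under the exact limit the counts and the criterion agree at n = 7–11, 20–22 and 27–33. They give opposite answers at n = 12–19 and 23–26 for the results listed, and at n = 1–6 because of the minimum of 3 events. The exact range depends on the interval method, which the plan does not name; a gap after patient 11 appears with every one-sided 80% method tried.

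The consequence is mainly delay. At a true rate of 20% the largest of the tabulated shortfalls is 0.15 by patient 19 (0.61 − 0.46), narrowing to 0.04 by patient 33 (0.76 − 0.72). These figures assume independent patients, a constant event rate and outcomes known as each patient is counted.

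Separately, and on either reading of the looks, the stated suspension probabilities at 30% overstate the rule's sensitivity by about 11, 7 and 2 percentage points.

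**What to change.** Reconcile the criterion and the counts in section 8.2, and name the interval method. Which of the two governs is for the sponsor to decide.

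- **If the criterion applies continuously:** the counts it implies, with a floor of 3 events stated openly, are 3 of 13, 4 of 19, 5 of 26 and 6 of 33, each *or fewer*. The cost is more suspensions at lower rates: by patient 33, 0.16 rises to 0.21 at a true rate of 10%, and 0.27 to 0.33 at 12%.
- **If the criterion applies only at 11, 22 and 33 patients:** say so, and stop presenting the counts as implementing it between those points. The stated look points then match the probabilities quoted. If the counts are also checked only at those points, suspension by patient 19 at a 20% rate is 0.38 rather than 0.46, so the text should say whether earlier suspension remains possible.

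In either case recompute the suspension probabilities for the rule adopted. For the counts as listed, the 30% figures should read 0.69, 0.87 and 0.97. The work is a few lines of text and one short calculation.

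### The suspension probabilities given for a 30% toxicity rate (0.80, 0.94, 0.99) are too high; the stated rule gives 0.69, 0.87 and 0.97

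*Combined protocol and SAP*

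**What the plan says.** The toxicity part of Section 8.2 sets a ceiling of 12% for grade 3 or higher infusion- or immune-related events. The ceiling counts as exceeded "if the lower level of a one-sided 80% confidence interval for immune-related or infusional" events lies above 12%. In operation, the study is suspended and referred to the DSMC when the number of patients with such an event reaches "3 out of the first 11 or fewer, 5 out of the first 22 or fewer, 6 out of the first 33 or fewer".

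Two sets of operating characteristics follow. At a true rate of 5%, the probability of suspension "after 11, 22, and 33 patients is approximately <0.02, 0.02, and 0.02, respectively". At a true rate of 30%, "the probability of suspension due to excess AE is approximately 0.80, 0.94, and 0.99, respectively". The source is given as "Probabilities of suspension estimated from 5,000 simulations". No other part of the document restates or corrects these figures.

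**The concern.** The first of the three 30% figures can be checked directly. It is the probability of at least 3 events in 11 patients at 30% each, a single binomial tail equal to 0.687, not 0.80. If the first figure is wrong, the other two are suspect because they accumulate from it.

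These are the only figures in the plan that show how reliably the trial would pause under excess toxicity. The patients are previously untreated and have indolent disease, and Sections 4.2.1 and 8.1 rest part of the rationale on low toxicity. Section 10.1 lists stopping rules among the things the oversight committees evaluate. A committee reading this sentence would think the rule more sensitive than it is, most of all at the first look.

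**Working it through.** **Inputs, all from Section 8.2.** Thresholds: at least 3 by patient 11, 5 by patient 22, 6 by patient 33. True rates: 5% and 30%. Stated results: <0.02, 0.02, 0.02 and 0.80, 0.94, 0.99. Simulation size: 5,000.

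**Method.** Exact binomial recursion. Each block of 11 patients adds a Binomial(11, p) count to the running total. Paths that reach the threshold are removed as suspended, and the rest carry forward. Checking the same thresholds after every patient gives the same cumulative results, because the event count never falls: reaching 3 at some point by patient 11 is the same event as having at least 3 at patient 11.

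**Step 1: the 5% line.** Cumulative suspension is 0.0152, 0.0171, 0.0198, which agrees with the plan. The separate single-look tails at 5% are 0.015, 0.004 and 0.005, which do not. The plan's figures are therefore cumulative.

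**Step 2: the thresholds.** Exact (Clopper-Pearson) one-sided 80% lower limits:

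| Look | At the threshold | One event fewer |
|---|---|---|
| 11 | 3/11: 14.3% | 2/11: 7.6% |
| 22 | 5/22: 14.4% | 4/22: 10.6% |
| 33 | 6/33: 12.04% | 5/33: 9.5% |

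So 3, 5 and 6 are the smallest counts whose limit exceeds 12%. The thresholds are not misprinted.

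**Step 3: the 30% line.**

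Look 1. P(0), P(1) and P(2) in 11 patients are 0.0198, 0.0932 and 0.1998. P(at least 3) = 1 − 0.0198 − 0.0932 − 0.1998 = 0.687.

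Look 2. Patients carried forward with 0, 1 or 2 events need at least 5, 4 or 3 more among the next 11, with probabilities 0.2103, 0.4304 and 0.6873. The added suspension probability is 0.0198 × 0.2103 + 0.0932 × 0.4304 + 0.1998 × 0.6873 = 0.1816. Cumulative: 0.869.

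Look 3. The states still running at 22 patients are 0 to 4 events, with probabilities 0.0004, 0.0037, 0.0166, 0.0423 and 0.0682. The same step adds 0.0975. Cumulative: 0.966.

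**Step 4: comparison.**

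| By patient | Stated at 30% | Exact at 30% | Gap (points) | Exact at 35% |
|---|---|---|---|---|
| 11 | 0.80 | 0.687 | 11.3 | 0.800 |
| 22 | 0.94 | 0.869 | 7.1 | 0.944 |
| 33 | 0.99 | 0.966 | 2.4 | 0.992 |

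**Step 5: simulation error.** The standard error is √(p(1 − p)/5000). At the exact values this is 0.0066, 0.0048 and 0.0026, so the gaps are about 17, 15 and 9 standard errors.

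**Step 6: other readings.**

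| Reading | At 30% | At 5% |
|---|---|---|
| Single-look tails | 0.687, 0.836, 0.959 | 0.015, 0.004, 0.005 |
| More than 3, 5, 6 events | 0.430, 0.714, 0.913 | not needed: 30% line already too low |
| First look moved to 13 patients | 0.798, 0.888, 0.969 | not needed: later 30% figures do not match |
| Clopper-Pearson limit after every patient | 0.768, 0.923, 0.978 | 0.077, 0.086, 0.089 |
| Wald limit after every patient from the third | 0.789, 0.934, 0.979 | 0.059, 0.072, 0.074 |

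The last reading comes within about a point of the printed 30% line but gives three or more times the stated 5% probabilities. No reading tried reproduces both lines.

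**The case against.** The arithmetic is not in dispute; the case on the other side is about weight. The study is suspended on event counts, and the counts are right on their stated basis. Correcting the sentence changes no threshold, sample size, endpoint or analysis. The ratio of miss rates at the last look (3.4% against 1%) sounds large but is 2.4 points, at a stage when accrual is complete. If suspension is counted only at the three looks, expected enrolment at 30% is 11 + 11 × 0.313 + 11 × 0.131 = 15.9 patients, against 11 + 11 × 0.20 + 11 × 0.06 = 13.9 from the printed figures, a difference of about two patients. Nor is the rule the only safeguard: Sections 5.8, 8.3.2.4 and 10.1 provide for early termination on adverse reactions, ongoing review of events, and DSMC review at least yearly. Section 10.1 does not say that the committees use these particular probabilities.

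All of that is fair, and it limits the point to the reported operating characteristics; the rule is not defective. It does not rescue the sentence, which tells the reader 0.80 where the rule gives 0.69.

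The match at 35% is close at all three looks, but it remains an inference. The document never mentions a 35% rate.

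**Conclusion.** The 30% line is wrong as written. For the stated rule, the cumulative probabilities of suspension are 0.69, 0.87 and 0.97, not 0.80, 0.94 and 0.99. The chance of not having suspended at a true 30% rate is 31% rather than 20% by patient 11, 13% rather than 6% by patient 22, and 3.4% rather than 1% by patient 33. The discrepancy that matters most in practice is the first.

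The result assumes independent patients with a common event rate and each patient's outcome known when the count is made. The plan's own 5% figures reproduce under the same assumptions. The thresholds and the 5% line stand.

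**What to change.** In Section 8.2, replace the three probabilities for a 30% true rate with approximately 0.69, 0.87 and 0.97, and state that they are cumulative. The authors should check which rate their simulation used. If it was 35%, the present figures can be kept as a further line under that label, but relabelling alone would leave 30% with no reported figure. The suspension rule needs no change. The cost is one sentence and a short rerun, and the stated protection becomes somewhat less favourable.
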